#### **End Point and Data Analysis:**

##### Primary Outcome

- Mortality at 24 hrs, 48 hrs, and 28 days

##### Secondary Outcomes

- Total amount and types of blood products transfused in 24 and 48 hours
- Total amount of estimated blood loss
- Occurrence of thromboembolic events

##### Pre-defined subgroup: Traumatic Brain Injury patients

- Glasgow Coma Scale less than or equal to 8.

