#### **Design: Retrospective Comparison and Prospective Cohort Study**

Four groups of patients will be utilized in this study as follows:

**A: Hospital Group:** this group will receive both doses of TXA according to the draft protocol upon arrival to the participating trauma center. No TXA will be given in the field to this patient grouping. 200 patients shall be enrolled in this group in a prospective observational study format.

**B: Air Transport Group:** This group will receive the first dose of TXA according to the draft protocol on scene or during the flight by a licensed flight RN or licensed flight physician. The second dose of TXA will be administered upon arrival at the participating trauma center. 200 patients shall be enrolled in this group in a prospective observational study format.

**C: Paramedic Group:** These patients will receive their first dose of TXA according to the draft protocol in the field by licensed paramedics from participating agencies. The second dose of TXA will be

administered upon arrival at the participating trauma centers. 200 patients shall be enrolled in this group in a prospective observational study format.

**D: Control Group:** 200 patients, transported by ambulance or by air, with similar injury severity and hemodynamics shall be randomly chosen from the previous five years of the trauma registry at the participating trauma center. These patients shall then be compared to Group A, B and C noted above in a retrospective comparison.

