**Inclusion criteria:**

The hospital and prehospital use of TXA should be considered for all trauma patients that meet **any** of the following criteria:

- Blunt or penetrating trauma with signs and symptoms of hemorrhagic shock.
- Systolic blood pressure of less than 90 mmHg at scene of injury, during air or/and ground medical transport, or on arrival to designated trauma centers
- Any Sustained Blunt or Penetrating injury within 3 hours
- Patients who are considered to be high risk for significant hemorrhage
  - Estimated blood loss of 500 milliliters in the field accompanied with HR >120.
  - Bleeding not controlled by direct pressure or tourniquet.
  - Major amputation of any extremity above the wrists and above the ankles.

[figure not shown]

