### **Data collection:**

Baseline characteristics

- Time of injury to TXA
  - (1st and 2nd dose)
- Demographics: Age, Gender, Race
- Vital Signs: five sets (pre-hospital, during infusion, post-infusion, during second infusion, post-infusion)
  - Heart rate, respiratory rate, body temperature, blood pressure, capillary refill
- Glasgow Coma Scale (pre-treatment, 24 hours, 48 hours)
  - ≤8, 9-12, 13-15

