### **Analysis Measures**

- Survival at 24 hours, 48 hours, and 28 days
- Cause of death (hemorrhage, other causes)
- Mechanism of injury (blunt, penetrating, combination of blunt and penetration, amputation)

- Area of injury
  - Head, chest, abdomen, extremity, multiple areas
- Blood product Used:
  - Packed red blood cells, fresh frozen plasma, platelets, cryoprecipitate.
- Estimated blood loss
  - Pre-hospital and hospital estimate, operating room estimate, and chest tube output
- Number of transfused unit(s) of blood products (<2 units, 2-4 units, >4 units i.e. massive transfusion.
- Time to emergency care: Time from EMS encounter to emergency department (ED), time spent in emergency department, time from ED arrival to operating room.
- Hospital length of stay: Intensive care unit length of stay, discharge disposition
- Ventilator days
- Adverse side effects, thromboembolic, seizures
- Deep venous thrombosis prophylaxis timing
- Result of drug test and medications that may falsely alter patients pulse during the initial evaluation and resuscitation

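### The traumatic brain injury subgroup is defined only by a GCS of 8 or less, with no head injury required and no GCS reading named, so its result cannot be attributed specifically to brain injury

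*Combined protocol and SAP*

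**What the plan says.** The plan names one subgroup, "Pre-defined subgroup: Traumatic Brain Injury patients", and gives a single line beneath it: "Glasgow Coma Scale less than or equal to 8". It adds no anatomical, imaging or diagnostic criterion and no time point.

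Three other parts of the plan bear on that line:

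- Data collection lists "Glasgow Coma Scale (pre-treatment, 24 hours, 48 hours" as the readings to be taken.
- Analysis Measures collects area of injury as "Head, chest, abdomen, extremity, multiple areas". The subgroup rule does not refer to it.
- Inclusion criteria admit "Blunt or penetrating trauma with signs and symptoms of hemorrhagic shock". No entry criterion requires a head injury. The Exclusion criteria remove penetrating cranial injury and brain injury with exposed brain matter.

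The Design section sets when the first dose is given. For Group A, "No TXA will be given in the field to this patient grouping"; both doses follow arrival. Group B is dosed "on scene or during the flight by a licensed flight RN or licensed flight physician". Group C is dosed "in the field by licensed paramedics from participating agencies". Group D is sampled from the previous five years of the trauma registry and has no study treatment time.

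**The concern.** The label is a diagnosis, while the rule is a level of consciousness. In bleeding trauma patients a low GCS can have causes other than brain injury, such as poor perfusion, intoxication or sedation. That is general clinical reasoning; the documents do not state it. As the rule is written, a patient with an isolated abdominal or limb injury and a GCS of 8 would count as a TBI patient.

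The Background discusses a randomized trial of TXA in brain injury and raises a possible role for the drug in severe brain trauma with coagulopathy. A result reported under this label would therefore be read as evidence on that question.

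The unnamed reading adds a second problem. Mortality at 24 h, 48 h and 28 days is the primary outcome, and who belongs to the subgroup, and whether they can die within the outcome window, depends on which GCS is used.

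**Working it through.** The plan attaches no figure to this subgroup, so there is nothing to reproduce. The target of 200 per group (Statistical analysis) is used below only as a denominator.

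**1. Label, rule and population.** The label is TBI. The rule is GCS of 8 or less. The population is hemorrhagic-shock trauma of any body region. The one collected item that could identify head injury, area of injury, is not part of the rule. If that item is recorded as a single choice, a head injury in a patient with several injured regions is entered as multiple areas and cannot be recovered from the item later. The plan does not say whether the categories are exclusive.

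**2. The three readings.**

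| Reading | When it falls | Consequence |
|---|---|---|
| Pre-treatment | A: before a dose given on arrival. B: on scene or in flight. C: in the field. D: no treatment time to anchor it | The same patient could fall in or out of the subgroup depending on group. A vs B, A vs C and A vs D, three of the four planned comparisons, are affected |
| 24 h | After treatment; patients alive at 24 h | 24 h mortality is zero by construction |
| 48 h | After treatment; patients alive at 48 h | 24 h and 48 h mortality are both zero by construction |

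**3. How mixed might the subgroup be?** All rates here are assumptions, because the documents give none. Let h be the share of the cohort with TBI (20–50%), a the probability of GCS ≤ 8 given TBI (30–50%), and b the same probability without TBI (5–20%).

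TBI share of subgroup = h·a / [h·a + (1 − h)·b]

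- Lowest (h = 0.2, a = 0.3, b = 0.2): 0.06 / (0.06 + 0.16) = 27%.
- Highest (h = 0.5, a = 0.5, b = 0.05): 0.25 / (0.25 + 0.025) = 91%.

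Subgroup size per group = 200 × [h·a + (1 − h)·b]

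- Smallest (h = 0.2, a = 0.3, b = 0.05): 200 × 0.10 = 20.
- Largest (h = 0.5, a = 0.5, b = 0.2): 200 × 0.35 = 70.

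**4. Effect of reading time alone, if pre-treatment is used.** Fix h = 0.3 and a = 0.4, and let only b differ between a field reading and an arrival reading.

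- b = 0.05: 0.12 / 0.155 = 77%.
- b = 0.10: 0.12 / 0.19 = 63%.
- b = 0.20: 0.12 / 0.26 = 46%.

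Under these inputs, the make-up of the subgroup would differ between groups through timing alone.

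**5. Dilution.** Let m be the share of the subgroup without head injury, equal in the groups compared. Suppose a 10-point difference exists in TBI patients and none in the others. The observed difference is then 10 × (1 − m): 8.0, 6.5 and 5.0 points for m = 0.20, 0.35 and 0.50. If the effect in patients without head injury is not zero, the distortion can go in either direction.

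**6. Precision for scale.** With p = 0.5 assumed, the 95% half-width for a difference in mortality is 1.96 × √(0.5/n): 31 points at n = 20 per group and 17 points at n = 70.

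**The case against.** The strongest reply is that the heading is itself a criterion, so the subgroup is TBI patients who also have a GCS of 8 or less. The text allows that reading, but it is the less natural one, since the bullet is the only criterion stated. It also leaves the gap open, because the plan then does not say how TBI is ascertained.

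A second reply is that Data collection lists GCS among baseline characteristics, which favours the pre-treatment reading. That is fair, but it does not settle the matter, since the same line includes the 24 h and 48 h values. The difference in timing between groups is therefore conditional on the pre-treatment reading being the one used.

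A third reply is that a dilution of 2 to 5 points is small beside a half-width of 17 to 31 points. This stands as a limit on the dilution figures. It does not answer the problem of labelling, or the zero mortality that a later reading would produce.

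A reader might also infer more than the documents support:

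- That the result will not be about brain injury at all. Under some of the assumptions above, the subgroup is mostly TBI.
- That the rule mainly selects the deepest shock. Nothing in the documents shows this.
- That the drug-test item in Analysis Measures shows concern about consciousness. The plan ties it to effects on pulse.
- That everything needed for a better definition is already collected. A first prehospital GCS and a head-region severity score are not listed items.

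**Conclusion.** The concern holds in this form: as written, the subgroup is a mixture of patients with and without head injury, of unknown make-up, and a finding in it cannot be attributed specifically to TBI. That rests on the text of the plan, plus the general clinical premise that GCS can be low without head injury. It does not depend on the assumed rates. The 27–91% share and the 8.0, 6.5 and 5.0-point figures only illustrate the possible scale.

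The reading must also be named, because none of the three now collected is free of difficulty. The zero mortality from a 24 h or 48 h reading is a matter of definition, given that GCS is scored in living patients and the plan has no rule for those who died. Non-comparability between groups follows only if the pre-treatment reading is used.

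The whole-cohort mortality analysis is unaffected. This is a change that should be made, but the study does not fail without it.

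**What to change.** - Define the subgroup as a recorded head injury (area of injury head, or multiple areas including the head) **and** GCS of 8 or less at one named reading obtainable in all four groups.
- Choose that reading explicitly. Two candidates are the first recorded GCS on EMS contact and the first on emergency department arrival. The EMS reading precedes the first dose in A, B and C, but may be missing in A and D. The arrival reading may be easier to obtain, but in B and C it follows the start of treatment.
- State a rule for missing GCS values, and apply it identically in every group.
- Record area of injury as check-all-that-apply, so that head injury within multiple areas can be identified.
- Report patients with GCS of 8 or less and no recorded head injury separately.

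The cost is a rewritten definition, one changed data item, possibly one added GCS field for some groups, and a check that the registry holds the chosen reading and injury area for Group D. The subgroup becomes smaller and its estimates less precise. A recorded head injury is not the same as a brain injury, so some misclassification would remain; a diagnosis or severity code would reduce it, but would be a new data item.
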